1.8. Compliance

This study will be conducted in compliance with this protocol, GCP, and all applicable regulatory requirements.

2. OBJECTIVES AND ENDPOINTS

Study Objectives	Study Endpoints

Primary objective:
 
 To assess the efficacy of filgotinib, GS-9876, and GS-4059 in adult subjects with active SjS 	
Primary endpoint:
 
The primary endpoint is the proportion of subjects fulfilling protocol-specified response criteria at Week 12, as compared to baseline.
 
Response is defined as follows:
 
 For subjects with elevated hsCRP (defined as ≥ 1.5 upper limit of normal (ULN) of hsCRP) at Day 1, subjects are considered to be a responder if they achieve all of the following : 
 $\geq 20\%$ improvement in hsCRP $\geq 20\%$ improvement in at least 3 out of 5 subject reported, SjS related visual analog scales (VAS; subject's assessment of global disease, pain, oral dryness, ocular dryness and fatigue) no worsening (defined as > 30 mm increase from baseline) in any of the above VAS For subjects without elevated hsCRP (< 1.5 ULN of hsCRP) at Day 1, subjects are considered to be a responder if achieve all of the following: 
 no increase ≥ 1.5 ULN of hsCRP $\geq 20\%$ improvement in at least 3 out of 5 subject reported, SjS related VAS (subject's assessment of global disease, pain, oral dryness, ocular dryness and fatigue) no worsening (defined as > 30 mm increase from baseline) in any of the above VAS

Secondary objectives:
 
 To assess the safety and tolerability of filgotinib, GS-9876, and GS-4059 in adult subjects with active SjS To assess the effect of filgotinib, GS-9876, and GS-4059 on patient reported outcomes in active SjS, including fatigue, disability, and quality of life 	
Secondary endpoints:
 
 Change from baseline in ESSDAI and ESSPRI at Weeks 12 and 24.

Study Objectives	Study Endpoints

The exploratory objectives of this study are:
 	
The exploratory endpoints of this study are:
 

3. STUDY DESIGN

[figure not shown]
3.1. Study Design

Adult male and female subjects who provide written, informed consent will enter a Screening period (28 days) during which they will be evaluated for eligibility, based on the Inclusion/Exclusion criteria.

At Day 1, eligible subjects will be randomized to study drug (see Section 3.2). Subjects will return to the study site for scheduled study visits at Weeks 2, 4, 8, 12, 18, 24, 26, 28, 32, 36, 42 and 48. After completion of the Week 24 assessments and procedures, subjects on placebo will be re-randomized 1:1:1 to filgotinib, or GS-9876, or GS-4059, in a blinded fashion. Dosing will continue through Week 48.

Subjects who discontinue study drug for any reason (other than noncompliance) may continue to participate in scheduled study visits and procedures, as long as deemed medically appropriate by the investigator. Subjects who discontinue all study participation will have an early termination (ET) visit; these subjects, and those who complete the study, should return to the study site for a follow-up visit, 4 weeks after the last dose of study drug (subjects who have discontinued study drug \geq 4 weeks prior to the ET/Week 48 visit, do not need a follow up visit).

Figure 3-1. Study Design Schematic

For details regarding dosing and blinding, see Section 5.7.

For details regarding concomitant and excluded medications, see Section 5.8.

For study visit schedule and procedures, including clinical laboratory tests and **CCI**, see Schedule of Activities in Section 6 and Appendix 2.

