At the Week 24 visit, subjects on placebo will be re-randomized 1:1:1, in a blinded fashion, to daily oral filgotinib (200 mg), GS-9876 (30 mg), or GS-4059 (40 mg) without further stratification. Dosing and assessments for all subjects will continue through Week 48.

CCI
[REDACTED]

Subjects who interrupt or permanently discontinue study drug dosing will continue the study visits, procedures, and assessments, if deemed medically appropriate by the investigator.

Number of Subjects Planned:

Approximately 140 adult subjects with active SjS

Target Population: Male and female subjects with active SjS between 18 and 75 years of age (inclusive) at the time of consent

Duration of Treatment: Up to 48 weeks of dosing

Diagnosis and Main Eligibility Criteria: Subjects must meet the all eligibility criteria participate in this study. For a complete list of study inclusion and exclusion criteria, please refer to Sections 4.2 and 4.3, respectively.

- Male or female subjects between 18 and 75 years of age (inclusive)
- Diagnosed with SjS according to American European Consensus Group (AECG) classification
- Active SjS as defined by an ESSDAI ≥ 5
- Seropositivity for antibodies to SjS-associated antigens A and B (anti-SSA or anti-SSB)
- No concurrent treatment with any bDMARD (washout as per protocol Section 5.8)

Study Procedures/
Frequency: Participating subjects will visit the clinical study center at Screening, Day 1, Weeks 2, 4, 8, 12, 18, 24, 26, 28, 32, 36, 42 and 48 or early termination (ET) plus follow up visit.

At Day 1, after the subject's eligibility for the study has been confirmed, the subject will be randomized into the study to receive filgotinib (200 mg), GS-9876 (30 mg), GS-4059 (40 mg), or PTM.

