3.4. Criteria for Interruption and Discontinuation Criteria

If a subject discontinues study dosing (for example, as a result of an AE), every attempt should be made to keep the subject in the study and continue to perform the required study-related follow-up and procedures. If this is not possible or acceptable to the subject or investigator, the subject may be withdrawn from the study. In these cases, an Early Termination visit should be performed as soon as possible.

CCI

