3.4.2. Study Drug Discontinuation Considerations

The Medical Monitor should be consulted prior to study drug discontinuation whenever feasible.

Study medication should be permanently discontinued in the following instances:

- Any opportunistic infection
- Any serious infection that requires antimicrobial therapy or hospitalization, or any infection that meets SAE reporting criteria.
- Complicated herpes zoster infection (with multi-dermatomal, disseminated, ophthalmic, or CNS involvement)
- Unacceptable toxicity, or toxicity that, in the judgment of the investigator, compromises the subject's ability to continue study-specific procedures or is not considered to be in the subject's best interest
- Need for prohibited concomitant medication (see Section 5.8)

- Subject request to discontinue for any reason
 - Subject noncompliance, as per judgment of investigator
 - Request from Gilead, a regulatory agency or an IRB or IEC
 - Female subject becomes pregnant during the study; refer to Section 7.7.2.1
 - Positive HCV VL
 - Investigator discretion
 - Laboratory criteria:
After becoming aware of any of the below described abnormal laboratory values at any time, an unscheduled visit should occur within 3 to 7 days, with the exception of creatinine clearance which should be retested within 7 to 14 days. Retest may be obtained sooner if medically indicated per investigator judgment. If the laboratory abnormality is confirmed by the retest, then study medication should be discontinued and further care of the subject should be directed per the investigator.
 - total white blood cell (WBC) count < 2000 cells/mm³ (SI: < 2.0x10⁹ cells/L)
 - neutrophil count < 1000 neutrophils/mm³ (SI: < 1.0x10⁹ cells/L)
 - hemoglobin < 8.0 g/dL (SI: < 80 g/L)
 - platelet count < 75,000 platelets/mm³ (SI: < 75.0x10⁹ cells/L)
 - AST or ALT elevation:
 - > 3xULN with at least 1 total bilirubin value >2xULN
 - > 3xULN with elevated international normalized ratio (INR)
 - > 5xULN, regardless of total bilirubin or accompanying symptoms
- Note:** For the above described AST or ALT elevations, additional investigations (such as: review of ethanol, recreational drug use, dietary supplement consumption; testing for acute hepatitis A, B or C infection and biliary tract imaging) should be promptly considered by the investigator; these subjects should be discussed with the study Medical Monitor.
- estimated creatinine clearance < 40 mL/min based on the Cockcroft-Gault formula

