5.1.1. Procedures for Breaking Treatment Codes

In the event of a medical emergency where breaking the blind is required to provide medical care to the subject, the investigator may obtain the individual subject treatment assignment directly from the IWRS system. Gilead recommends, but does not require, that the investigator contact the Gilead Medical Monitor before breaking the blind. Treatment assignments should remain blinded unless that knowledge is necessary to determine emergency medical care for the subject. The rationale for unblinding must be clearly explained in source documentation and on the electronic case report form (eCRF), along with the date on which the treatment assignment was unblinded. The investigator is requested to contact the Gilead Medical Monitor promptly in case of any treatment unblinding.

Blinding of study treatment is critical to the integrity of this Phase 2 clinical trial and therefore, if a subject's treatment assignment is disclosed to the investigator, the subject will be discontinued from the trial.

Gilead Pharmacovigilance and Epidemiology (PVE) may independently unblind cases for expedited reporting of suspected unexpected serious adverse reactions (SUSARs) to Regulatory Authorities.

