3.9. Efficacy Estimands

Three efficacy estimands: a treatment-policy estimand, a hypothetical estimand and a composite estimand, are defined for the primary and secondary efficacy endpoints.

The **treatment-policy estimand** is the primary estimand for the primary and secondary efficacy endpoints.

1) Population: Subjects in the FAS

- 2) Variable: Primary and secondary endpoints
- 3) Intercurrent events: The occurrence of an intercurrent event is irrelevant. All observed values will be used regardless of occurrence of an intercurrent event

The **hypothetical estimand** is defined as following. This is the supportive estimand for the primary and secondary efficacy endpoints.

- 1) Population: Subjects in the Full Analysis Set (FAS).
- 2) Variable: Primary and secondary endpoints
- 3) Intercurrent events: The following intercurrent events are taken into account:
 - Subject takes prohibited medication
 - Subject changes the dose of the medication required to be stable per protocol
 - Subject discontinues from study treatment

The **composite estimand** is defined as following. This is the supportive estimand for the primary and secondary efficacy endpoints.

- 1) Population: Subjects in the Full Analysis Set (FAS).
- 2) Variable: Primary and secondary endpoints
- 3) Intercurrent events: The following intercurrent events are taken into account:
 - Subject takes prohibited medication
 - Subject changes the dose of the medication required to be stable per protocol
 - Subject discontinues from study treatment

The estimators associated with each of these estimands are described in [Table 3](#) of Section 6.

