6.3. Analysis for the Primary Efficacy Endpoint

6.3.1. Primary Analysis of Primary Endpoint

In the primary analysis, the primary outcome in each active treatment group will be compared to the outcome in the placebo group using a superiority test at the 2-sided 0.05-level. The following null hypotheses will be tested (vs. the respective alternative hypotheses):

- H01: There is no difference in the responder rate between filgotinib 200 mg group and placebo group at Week 12
- H02: There is no difference in the responder rate between lanraplenib 30 mg group and placebo group at Week 12
- H03: There is no difference in the responder rate between tirabrutinib 40 mg group and placebo group at Week 12

The analyses will be performed using Cochran Mantel Haenszel (CMH) test adjusted for the randomization stratification factors. If CMH test stratified by both stratification factors is not appropriate due to small cell counts then the levels of the stratification by ESSDAI scores will be pooled, and the analysis will be stratified only by use of concurrent immunomodulatory drugs at baseline. Each of the three hypotheses will be tested separately at the 2-sided, 0.05-level.

The primary analysis will be based on the Treatment Policy Estimand, with missing values imputed by multiple imputation method described in Section 6.1.

The number and percentage of responders in each treatment group as well as 95% confidence intervals (CIs) will be presented for each visit.

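### Protocol sections disagree on follow-up after a noncompliance stop, and the code-break rule halts collection of outcomes that the primary treatment-policy estimand needs

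*Protocol*

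**What the plan says.** **Follow-up after study drug stops.**
- Protocol 3.1: "Subjects who discontinue study drug for any reason (other than noncompliance) may continue to participate in scheduled study visits and procedures", as long as the investigator finds it medically appropriate. SAP 1.2 repeats the sentence.
- Protocol Synopsis: "Subjects who interrupt or permanently discontinue study drug dosing will continue the study visits, procedures, and assessments, if deemed medically appropriate by the investigator".
- Protocol 3.4, on subjects who stop dosing: "every attempt should be made to keep the subject in the study and continue to perform the required study-related follow-up and procedures". Withdrawal is the fallback if this is not possible or not acceptable to the subject or investigator.
- Protocol 3.4.2 lists among the reasons for permanent discontinuation of drug: "Subject noncompliance, as per judgment of investigator". It sets no threshold.

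**Code breaks.** Protocol 5.1.1 limits unblinding to medical emergencies and gives the integrity of blinding as its reason. It then states that if a subject's "treatment assignment is disclosed to the investigator, the subject will be discontinued from the trial". Unblinding by the sponsor's pharmacovigilance group for expedited reporting is described separately.

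**Estimand and missing data.** SAP 3.9 makes treatment policy the primary estimand for the primary and secondary endpoints: "All observed values will be used regardless of occurrence of an intercurrent event". SAP 6.3.1: "The primary analysis will be based on the Treatment Policy Estimand, with missing values imputed by multiple imputation method described in Section 6.1". For binary variables, SAP 6.1 specifies 20 imputed datasets from logistic regression models and names only the stratification factors as content of the model. SAP 6.6 records that the estimands were added relative to the protocol.

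**The concern.** A treatment-policy estimand is only as good as the data collected after the intercurrent event. Stopping for noncompliance and emergency unblinding are both plausibly related to tolerability or lack of effect. Ending follow-up at either point turns outcomes that could have been observed into missing ones, and they may be missing for reasons linked to response.

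The imputation model, as written, names no variable for drug discontinuation, adherence or unblinding. It has no stated means of reflecting that these subjects are off drug. Nor is there much slack in numbers. The sample-size sections need about 35 evaluable subjects per arm and plan to enroll about 35, and Protocol 3.4.2 does not replace subjects who stop drug. One subject is 1/35 = 2.9% of an arm.

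**Working it through.** **1. Sections side by side.**

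| Section | Trigger | Follow-up | Noncompliance exception |
|---|---|---|---|
| Synopsis | drug interrupted or stopped | will continue, if medically appropriate | none |
| Protocol 3.4 | drug stopped | every attempt to retain | none |
| Protocol 3.1, SAP 1.2 | drug stopped | may continue, if medically appropriate | yes, by implication |
| Protocol 5.1.1 | assignment disclosed to investigator | out of the trial | not applicable |

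Rows 1 and 2 disagree with row 3 on noncompliant subjects. Noncompliance is also the odd one out elsewhere: Protocol 5.8 lets subjects withdrawn from drug over concomitant-medication doses keep attending visits. Row 4 has a different trigger. Its conflict is with SAP 3.9 and Table 3.

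**2. Effect on the estimator.** For the binary endpoint, SAP Table 3 gives the treatment-policy and hypothetical estimands the same estimator, a stratified CMH test after logistic-regression imputation. They differ only in whether data after the event are used. If no such data exist, both handle the subject in the same way, and the primary analysis no longer delivers treatment policy for that subject.

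**3. What the early termination (ET) rule recovers.** VAS and hsCRP are scheduled at Weeks 2, 4, 8 and 12 and at ET. SAP 3.8.2 assigns ET data to the next scheduled visit, so an exit between Weeks 8 and 12 can supply a Week 12 value. SAP 4.1 likewise counts an ET visit after Week 8 as Week 12 study completion. An exit before the Week 8 visit cannot supply one.

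**4. The plan's own figure.** The documents give no figure for these losses; the nearest is the sample size. With 70% vs 30%, two-sided 0.05 and 85% power, the pooled formula is n = [1.960 × √(2 × 0.5 × 0.5) + 1.036 × √(0.21 + 0.21)]² / 0.40² = 26.5, so 27 per arm (32 with continuity correction). The stated 35 is not reproduced, but it is conservative: power at 35 is 93.5% (89.5% corrected). At 31 per arm, about a 10% loss, it is 90.3% (84.6%). Bias matters more here than power.

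**5. Illustrative bias.** Let f be the share of an arm lost before Week 12, r the true response rate of those lost, and m the rate at which they are imputed. Then:

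bias in one arm = f × (m − r)

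bias in the difference = f_a(m_a − r_a) − f_p(m_p − r_p)

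Only the 70% and 30% planning rates come from the documents (Protocol 8.9, SAP 1.3). Here they stand for retained subjects. All f and r values are assumptions.

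*Arm-specific imputation (m_a = 0.70), losses on one active arm only:*

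| Share lost | r = 0.50 | r = 0.30 | r = 0 |
|---|---|---|---|
| 2 of 35 | 1.1 points | 2.3 points | 4.0 points |
| 10% | 2 points | 4 points | 7 points |
| 20% | 4 points | 8 points | 14 points |

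*Pooled imputation, 10% lost in every arm.* SAP 6.1 does not name arm in the model. Ignoring strata, with all three active arms at 70%, m = (3 × 0.70 + 0.30)/4 = 0.60.
- r = 0.30 in both arms: 0.10 × (0.60 − 0.30) − 0.10 × (0.60 − 0.30) = 0.
- r = 0.50 on active, 0.30 on placebo: 0.10 × 0.10 − 0.10 × 0.30 = −0.02, or 2 points against the drug.

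**The case against.** The strongest reply has four parts.

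**No sentence bars noncompliant subjects from visits.** The exclusion follows only from a parenthesis in a permissive sentence, and two other places point the other way. This stands. A reader might infer that the protocol has a settled rule ending their follow-up; the text supports only that its sections disagree.

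**Section 5.1.1 can be followed together with 3.4 and the Synopsis.** A reader might infer that it contradicts them, but they concern stopping drug and it concerns disclosure of the code. It also has a rationale, since the five VAS in the primary endpoint are patient-reported and knowledge of treatment could color them. This stands too. The conflict with the estimand remains, because treatment policy uses values observed after the event.

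**Safeguards exist.** ET data can fill Week 12 for exits after Week 8, although the sentence after that rule in SAP 3.8.2 withholds assignment in some cases. The composite estimand, a planned sensitivity analysis, counts data after treatment discontinuation, and missing data, as non-response. Both limit the problem. But earlier exits remain imputed in the primary analysis, and the composite estimand answers a different question in a supportive role.

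**Safety follow-up is not abandoned.** A reader might infer that removed subjects lose safety assessment. They keep the ET visit, with full examination, laboratory tests and ECG, and the 4-week follow-up visit where applicable. What they lose is the remaining scheduled visits.

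**Conclusion.** The concern holds as an inconsistency with a risk attached. Two things need correcting: the disagreement between sections about noncompliant subjects, and the clash between the code-break rule and the primary estimand. Together they risk avoidable, possibly informative, missing outcomes at Week 12, and likewise for the Week 24 secondary endpoints.

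It is tempting to conclude that the plan biases results toward the drug by a few points. The documents do not support that. They give no expected number of noncompliance stops or code breaks, no response rate for such subjects, and no statement on whether arm enters the imputation model. The 2 to 7 points at 10% loss require arm-specific imputation at 70% and losses confined to one active arm; other assumptions give zero or the opposite sign. That the missingness is informative is plausible but not shown. The point deserves action because it is cheap to prevent, not because a bias has been demonstrated.

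**What to change.** 1. Delete the parenthesis excepting noncompliance in Protocol 3.1 and SAP 1.2.
2. Revise Protocol 5.1.1 so that a code break is recorded as an intercurrent event and scheduled assessments continue where medically appropriate and the subject agrees. Any decision on study drug is left to the sponsor; this change concerns data collection only.
3. Reconcile the Synopsis, Protocol 3.1, 3.4 and 5.1.1 and SAP 1.2 with each other and with SAP 3.9. This includes their differing strength: will continue, may continue, every attempt.

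**Cost:** a wording amendment to both documents and a few visits already in the schedule. Some assessments will be made after unblinding and should be flagged in the data.

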3.2. Study Treatments

Following completion of screening assessments, eligible subjects will be randomized 1:1:1:1 in a blinded fashion to active investigational product or PTM:

- **Filgotinib 200 mg arm (n=35): filgotinib (1 x 200 mg tablet once daily) + PTM GS-9876 (1 x tablet once daily) + PTM GS-4059 (1 x tablet once daily)**
- **GS-9876 30 mg arm (n=35): PTM filgotinib (1 x tablet once daily) + GS-9876 (1 x 30 mg tablet once daily) + PTM GS-4059 (1 x tablets once daily)**
- **GS-4059 40 mg arm (n=35): PTM filgotinib (1 x tablet once daily) + PTM GS-9876 (1 x tablet once daily) + GS-4059 (1 x 40 mg tablet once daily)**
- **Placebo arm (n=35): PTM filgotinib (1 x tablet once daily) + PTM GS-9876 (1 x tablet once daily) + PTM GS-4059 (1 x tablet once daily)**

Randomization will be stratified by use of concurrent immunomodulatory drugs at baseline (Y/N: csDMARDs or corticosteroids), and the hematologic + biological component scores of the ESSDAI obtained at screening (combined score of <2 or ≥ 2).

3.3. Duration of Treatment

Subjects will be dosed for up to 48 weeks and will return for a Follow-Up Visit, 4 weeks after their last visit (Week 48 or ET); the Follow-Up Visit will not be performed if the subject has discontinued study drug ≥ 4 weeks prior to their final study visit.

3.4. Criteria for Interruption and Discontinuation Criteria

If a subject discontinues study dosing (for example, as a result of an AE), every attempt should be made to keep the subject in the study and continue to perform the required study-related follow-up and procedures. If this is not possible or acceptable to the subject or investigator, the subject may be withdrawn from the study. In these cases, an Early Termination visit should be performed as soon as possible.

CCI

3.4.1. Study Drug Interruption Considerations

The Medical Monitor should be consulted prior to study drug interruption when medically feasible.

Study drug interruption should be considered in the following circumstances; prior to resumption of study drug, the investigator should discuss the case with the Gilead medical monitor:

- Intercurrent illness that would, in the judgment of the investigator, affect assessments of clinical status to a significant degree.
- Subject is scheduled for emergency surgery (excluding minor skin procedures under local or no anesthesia); timing of study drug pausing should be determined in consultation with the Gilead medical monitor.
- If the subject has any signs or symptoms suggestive of infection (regardless of severity), study drug dosing should be immediately interrupted, and the medical monitor notified. Any subject who develops a new infection during the study should undergo prompt and complete diagnostic testing appropriate for an immunocompromised individual, and the subject should be closely monitored. Study treatment should not be resumed until the subject's event has resolved, per judgment of the investigator.

NOTE: During the time of study drug interruption for any of the above, the subject may continue to have study visits and to take part in procedures and assessments, if deemed medically appropriate by the investigator.

